To evaluate overall opinion of receiving and administering the injection at an infusion center by IC/ASA staff, participants and HIV care providers/clinical staff	
 
Summary of the overall opinion of administering the injection at an IC/ASA by IC/ASA staff other quantitative questionnaires prior to Month 1, at Month 3, and Month 8
 
		
	
 
Summary of overall opinion of receiving CABENUVA at an infusion center by participant other quantitative questionnaires at Month 1, Month 3, and Month 8.
 
		
	
 
Summary of overall opinion of referring patients to an IC/ASA center for CABENUVA injections by HIV care provider/clinical staff via other quantitative questionnaires at Month 1, Month 4 and Month 8
 
		
	
 
Qualitative interviews at Month 8 with participants, HIV care providers/clinical staff and IC/ASA staff
 
		
To evaluate fidelity to treatment and dosing window	Proportion of injections occurring within target window from target date (± 7 days of target date) through Month 8		
Other / Tertiary			
CCI			

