#### Type of Participant and Disease Characteristics

- 2 HIV-1 infected and have been prescribed CABNEUVA per the USPI. Participants can be enrolled:
  - If they have been taking oral VOCABRIA + EDURANT or other ART for approximately 1 month (at least 28 days) prior to Baseline/Month 1, or
  - Already taking CABENUVA prior to Baseline/Month 1 and the last injections
    were within a 1 month ± 7-day window or for every 2-month injections, the
    timing will vary they are receiving the initiation injections (1 month ± 7-day) or
    the continuation injections (2 months ± 7 days) per the USPI, or
  - Prescribed direct to inject and receive their 1st injection without an oral lead in at the Infusion Center on the last day of any other antiretroviral therapy.

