CABENUVA IM Injecti	ons initiated	at IC/ASA,	oost oral lea	ad-in (1 st inje	ections of C	ABENUVA a	at the IC/AS	SA)		The final oral doses of VOCABRIA + EDURANT, or other ART, should be taken on the same day when injections with CABENUVA are started.
•				· •						Questionnaires and procedures should be conducted prior to the injections.

Dragadura1	Baseline/			Treatme	nt Period (	Months)			E.D. 	Notes
Procedure 	Month 1 	2	3	4	5	6	7	8	E.D.º	Notes
Monthly Dosing (post oral lead-in)	Х	Х	Х	Х	Х	Х	Х	Х		IM dosing is expected to occur on the same date of the month as determined by Dose 1 - Treatment Target Date. Dosing window is (+ or -) a 7-day window
Every 2-month Dosing	Х	Х		Х		х		х		Dosing window for every 2-months is +/ - 7-days.
CABENUVA IM Conting subsequent injections a Note: To avoid having assessments (Month 8)	t the IC/ASA participants w	hose last in	jections are	at Month 7	return to the	e IC/ASA at	Month 8, th	ne end of stu		Questionnaires and interviews should be conducted prior to the injections.
Monthly Dosing	Х	Х	X	X	X	х	Х	х		The first study related CABENUVA injections at the IC/ASA should be started within 1 month (±7-day) after the last injections.  For participants switching from an every-2-month continuation injection schedule to a monthly continuation dosing schedule, follow the dosing instructions in the most recent USPI for CABENUVA, pl.
Every 2-month dosing (participants already receiving every 2-month dosing)	Х		Х		Х		х			Dosing window for every 2-month dosing is $\pm$ 7-days. For participants switching from a monthly continuation injection schedule to an every-2-month continuation injection dosing schedule follow the dosing instructions in the most recent USPI for CABENUVA.,

Procedure 	Baseline/			Treatme	ent Period (	(Months)		E.D.3	Notes	
Procedure.	Month 1 	2	3	4	5	6	7	8	E.D.	Notes
Concomitant medication review	Х	[====	======		======	======	======	====[]	х	The IC/ASA will note all new concomitant medications and send to the HIV care provider. Contraindicated medications and concomitant medications with a potential for a DDI per CABENUVA USPI will be recorded.
Adverse Event (AE) Review	Х	0====	======	======	======	======	======	====[]	х	See Section 10 for more information on the DAIDS grading scale, Section 10.3.7 for guidelines on assessment of causality, and Section 10.3.10 for AE reporting requirements
										Refer to the Annex 3 for definitions of AEs.

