Assessments (HIV1- RNA, Liver Chemistries, Other Labs Per POT)	Х	the HIV	care provid	der. All lab source do	be obtained reports must cumentation otherwise r	Х	The HIV care provider is responsible for monitoring and any follow-up of elevated HIV-1 RNA and liver chemistries in their PLWHIV and tet the IC/ASA know if there are any changes to the monthly or every-2-month injections. The F-care provider can request that the IC/ASA draw labs at any time or they can perform local labs a required.			
Study Treatment: All inj	ections will be	e administer	ed accordin	g to the CA	ABENUVA US	SPI				
CABENUVA IM Injection	s initiated at		The final oral doses of CAB + RPV, or other ART, should be taken on the same day when injections with CABENUVA are started. Questionnaires and procedures should be conducted prior to the injections.							
Monthly Dosing (Post Oral Lead-In)	X	Х	Х	Х	X	Х	Х	Х		IM dosing is expected to occur on the same date of the month as determined by Dose 1 - Treatment Target Date. Dosing window is ±7 days.
Every-2-month Dosing	Х	Х		Χ		Х		Х		Dosing window for every-2-months is \pm 7 days.
CABENUVA IM Continua subsequent injections a	•		already red	ceiving CAB	BENUVA inje	ections, and	who are to	get their		Questionnaires and interviews should be conducted prior to the injections.

Note: To avoid having participants whose last injections are at Month 7 return to the IC/ASA at Month 8, the end of study assessments (Month 8) will be completed at Month 7. Questionnaires and potential interviews will be completed at Month 8.										
Monthly Dosing	Х	X	X	Х	Х	Х	X	Х		The first study-related CABENUVA injections at the IC/ASA should be started within 1 month (±7 days) after the last injections. For participants switching from an every-2-month continuation injection schedule to a monthly continuation dosing schedule, follow the dosing instructions in the most recent USPI for CABENUVA.
Every-2-month Dosing (Participants Already Receiving Every-2-month Dosing)	X		X		Х		X			Dosing window for every-2-month dosing is ±7 days. For participants switching from a monthly continuation injection schedule to an every-2-month continuation injection dosing schedule follow the dosing instructions in the most recent USPI for CABENUVA.

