¹ Based on the normal approximation to the binomial distribution. Upper bound capped at 100% and lower bound capped at 0%.

² Injection appointments that result in shows were defined as an injection at visit N occurring during the target window. Baseline visits were excluded as no scheduled date was recorded. Participants who withdrew during the target window were counted as no shows.

³ Missed appointments were defined as any appointment for which no injection occurred among participants who reached the target window prior to study discontinuation.

⁴ No missed dose forms were completed, therefore participant and HIV care provider notification could not be determined.

⁵ Return rate was determined by counting the number of participants receiving an injection at visit N based on the number expected according to the number of participants at the previous visit.

⁶ Eligible participants included consented, declined study participation, not scheduled/lost to follow-up after referral. Eligible participants excluded those not receiving CABENUVA due to lack/change of insurance or cancellation by HCP, not enrolled due to site closure, not attending infusion center, and unknown and was prescribed CABENUVA every other month (before permitted in study) and <18 years of age.

 $^{^{7}}$ Target dates for injections were determined in accordance with the methodology implemented in the PLWHIV outputs. Abbreviations: CI = Confidence interval; HIV = human immunodeficiency virus; IC/ASA = infusion center/ alternate site of administration; IM = intramuscular; N/A = Not available; NE= Not estimable

A Phase 4, Open-label, Single-arm Study to Optimize Implementation of CABENUVA for the Treatment of HIV-1, for Administration in US Community-based Infusion Centers or Alternate Site of Administration

Table 7.2 IC/ASA Metric Reporting - Palmetto

Table 7.3 IC/ASA Metric Reporting - Medix

Table 7.4 IC/ASA Metric Reporting - Infusion Associates

Table 8. Distributional Characteristics of the Feasibility Composite Score

	Number of Clinics ¹	Missing	Mean	SD	Median (Q1, Q3)	Range (Min, Max)	95% Cl (Lower, Upper)	Cronbach's α²
Feasibility Composite Score ³	XX	XX	XX.X	XX	XX (X.X, X.X)	(X.X, X.X)	(X.X,X.X)	X.XX
FIM Score ⁴	XX	XX	XX.X	XX	XX (X.X, X.X)	(X.X, X.X)	(X.X,X.X)	X.XX
Consent Rate	XX	XX	XX.X	XX	XX (X.X, X.X)	(X.X, X.X)	(X.X,X.X)	X.XX
Show Rate	XX	XX	XX.X	XX	XX (X.X, X.X)	(X.X, X.X)	(X.X,X.X)	X.XX
Return Rate	XX	XX	XX.X	XX	XX (X.X, X.X)	(X.X, X.X)	(X.X,X.X)	X.XX

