--	---	-----------	-----------

If a participant switches between monthly and bi-monthly injection groups during the study, the participant will be summarized under the treatment group within which they began the study

Baseline target dosing date was determined as follows:

The last date of VOCABRIA + ENDURANT for patients on oral lead-in.

Previous injection date +1 month for participants on monthly CABENUVA regimen prior to the study.

Previous injection date + 2 months for participants on a bi-monthly CABENUVA regimen prior to the study. For participants on a planned bi-monthly CABENUVA regimen prior to the study receiving their first dose (loading dose), target date was injection date + 1 month.

Date of first injection for participants on neither oral lead-in nor previously using CABENUVA.

Target dosing date for follow-up visits were determined as follows:

Day of the month of baseline injection + 1 month for participants on monthly CABENUVA regimen.

Day of the month of baseline injection + 2 months for participants on a bi-monthly CABENUVA regimen.

For target injection dates occurring on the 29, 30th, or 31st in months without that day, the last day of the month was used. As fidelity is to be determined based on total number of injections given during the course of the study, injections not occurring due to participant withdrawal, loss-to-follow-up or missed injections prior to study discontinuation were set to missing.

Table 9. CABENUVA Adherence: days from the target dosing date at each study visit, Safety Set

		CABENUVA Monthly Injection (N=XX)	CABENUVA Bi- monthly Injection (N=XX)
Month 1 (days)	n	XX	XX
	Mean (SD)	XX.XX (XX.XX)	XX.XX (XX.XX)
	Median (Q1, Q3)	XX.XX (XX, XX)	XX.XX (XX, XX)
	Min, Max	XX.XX, XX.XX	XX.XX, XX.XX
Month 2 (days)	n	XX	XX
	Mean (SD)	XX.XX (XX.XX)	XX.XX (XX.XX)
	Median (Q1, Q3)	XX.XX (XX, XX)	XX.XX (XX, XX)
	Min, Max	XX.XX, XX.XX	XX.XX, XX.XX
Month 3 (days)	n	XX	XX
	Mean (SD)	XX.XX (XX.XX)	XX.XX (XX.XX)
	Median (Q1, Q3)	XX.XX (XX, XX)	XX.XX (XX, XX)
	Min, Max	XX.XX, XX.XX	XX.XX, XX.XX
Month 4 (days)	n	XX	XX
	Mean (SD)	XX.XX (XX.XX)	XX.XX (XX.XX)
	Median (Q1, Q3)	XX.XX (XX, XX)	XX.XX (XX, XX)
	Min, Max	XX.XX, XX.XX	XX.XX, XX.XX
	n	XX	XX

	Mean (SD)	XX.XX (XX.XX)	XX.XX (XX.XX)	
Month 5 (days)	Median (Q1, Q3)	XX.XX (XX, XX)	XX.XX (XX, XX)	
(44)	Min, Max	XX.XX, XX.XX	XX.XX, XX.XX	
	n	XX	XX	
Month 6	Mean (SD)	XX.XX (XX.XX)	XX.XX (XX.XX)	
(days)	Median (Q1, Q3)	XX.XX (XX, XX)	XX.XX (XX, XX)	

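### The fidelity target-date rule fits only one of the two every-2-month schedules in Annex 1, so on-schedule injections of participants who start that regimen in the study are scored out of window

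*SAP*

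**What the plan says.** The protocol (Section 3) defines fidelity as a secondary endpoint: "Proportion of injections occurring within target window from target date (± 7 days of target date) through Month 8".

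The target dates are defined only in the participant SAP, in the footnotes to Table 8, repeated under Table 9. For follow-up visits on the every-2-month regimen the rule is: "Day of the month of baseline injection + 2 months for participants on a bi-monthly CABENUVA regimen". The monthly regimen has the same rule with one month in place of two. The footnotes make one 1-month exception for the every-2-month regimen. It is part of the baseline target and applies to participants on a planned bi-monthly regimen before the study and "receiving their first dose (loading dose), target date was injection date + 1 month".

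Protocol Annex 1, reproduced in Appendix 7.1 of the clinical SAP, has two every-2-month rows:

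- Injections initiated at the IC/ASA: Months 1, 2, 4, 6, 8. The note reads "Dosing window for every 2-months is +/ - 7-days".
- Participants already receiving every-2-month dosing: Months 1, 3, 5, 7, with the same 7-day window.

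Inclusion Criterion 2 (protocol Section 4.2.1.1) also separates a 1-month initiation interval from a 2-month continuation interval, and it admits both oral lead-in and direct-to-inject starters.

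The staff SAP imports the rule. Footnote 7 to its Table 7.1, attached to the fidelity metric, says "Target dates for injections were determined in accordance with the methodology implemented in the PLWHIV outputs".

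**The concern.** A single interval of two months from baseline matches the continuation row of Annex 1 but not the initiation row, whose first interval is one month. The only 1-month provision in the SAP concerns people first dosed before they joined. Nothing in the documents gives a Month 2 target to a participant whose first injection is given in the study, although the Table 9 shell has a bi-monthly cell for Month 2.

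At stake is a one-directional error in a secondary endpoint: a participant who follows Annex 1 exactly is reported as off schedule. The error carries into the staff SAP fidelity metric. It may also reach the show rate, which counts injections inside a target window (staff SAP Table 7.1, footnote 2) and is a component of the feasibility composite, but the SAP does not say whether that window uses the same dates. The footnotes are in the past tense, so outputs may already have been produced with this rule.

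**Working it through.** The documents state no fidelity percentage, so there is no figure to reproduce. The check is whether the rule returns each Annex 1 schedule when every injection is given on its due date.

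**Inputs.** Schedules and the 7-day window come from Annex 1; the target rule and the end-of-month convention from the Table 8 footnotes. The Month 1 injection of a starter is on target. Without oral lead-in, the footnote sets its target to the date of that injection. With oral lead-in, the target is the last oral dose, which Annex 1 places on the same day.

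The footnote does not say how the two months iterate, so two readings were scored:

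- Anchored: follow-up targets at baseline + 2, 4, 6, 8 months.
- Rolling: each target is the previous injection + 2 months.

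**Example, starter with baseline 10 January 2023:**

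| Visit | Injection | Anchored target | Days | Rolling target | Days |
|---|---|---|---|---|---|
| Month 2 | 10 Feb | 10 Mar | -28 | 10 Mar | -28 |
| Month 4 | 10 Apr | 10 May | -30 | 10 Apr | 0 |
| Month 6 | 10 Jun | 10 Jul | -30 | 10 Jun | 0 |
| Month 8 | 10 Aug | 10 Sep | -31 | 10 Aug | 0 |

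**All 730 baseline dates, 1 January 2022 to 31 December 2023:**

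- Continuation row: 4 of 4 in window on both readings, for every date.
- Initiation row, anchored: Months 2, 4, 6 and 8 are each 28 to 31 days early and never in window. Score 1 of 5.
- Initiation row, rolling: Month 2 is 28 to 31 days early and never in window; Months 4, 6 and 8 are within 0 to 2 days. Score 4 of 5.
- Initiation row, scored against the nearest date in the two-monthly series from baseline: Months 2, 4, 6 and 8 still miss by 28 to 31 days.
- Targets taken from the participant's own Annex 1 row: 5 of 5 for starters, 4 of 4 for continuers.

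The Month 2 injection therefore lies 28 - 7 = 21 to 31 - 7 = 24 days beyond the window edge.

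**Effects that need no assumed share of starters:**

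- Table 9: apart from regimen switchers, only in-study starters have a bi-monthly Month 2 injection, so perfect adherence shows a mean of about -30 days (range -31 to -28).
- Table 8: each perfectly adherent starter moves from row 0 to row 1 (rolling) or row 4 (anchored).

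**Group percentage under perfect adherence.** Let s be the share of starters (5 injections each) among bi-monthly participants, the rest contributing 4 each. Month 1 is counted. Rolling: 4/(4 + s). Anchored: (4 - 3s)/(4 + s). The values of s are assumptions.

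| s | Rolling | Anchored |
|---|---|---|
| 10% | 4/4.10 = 97.6% | 3.70/4.10 = 90.2% |
| 25% | 4/4.25 = 94.1% | 3.25/4.25 = 76.5% |
| 50% | 4/4.50 = 88.9% | 2.50/4.50 = 55.6% |

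**Pooled metric in the staff SAP**, assuming half of participants are monthly (8 injections each). The numerator per participant is 0.5 × 8 plus 0.5 × 4 (rolling) or 0.5 × (4 - 3s) (anchored); the denominator is 0.5 × 8 + 0.5 × (4 + s).

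| s | Rolling | Anchored |
|---|---|---|
| 25% | 6/6.125 = 98.0% | 5.625/6.125 = 91.8% |
| 50% | 6/6.25 = 96.0% | 5.25/6.25 = 84.0% |

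**The case against.** The best defence is that the footnote is shorthand for programming that cannot be seen. Taken literally, even the monthly line gives no target after Month 2. Because the rule is built on the day of the month, it could mean that day applied in each scheduled visit month, which would remove the mis-scoring. That reading cannot be excluded from the code, but it leaves the SAP's distinction between one month and two months with no function, so it is not what the text says.

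A second objection is that the anchored reading compares the Month 8 injection with a date in Month 9, which is outside the endpoint and has no row in Table 9. That is true, but the result does not depend on that pairing: against the nearest date in the anchored series, the same injections still miss by 28 to 31 days.

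Third, the study-level effect depends on a starter share that the documents do not give, fidelity is descriptive, and on the rolling reading the shift is modest. This stands as a limit on size. It does not affect the finding that Month 2 fails on both readings and for every baseline date. The link to the show rate is also unproven and is put only as something to check.

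**Conclusion.** The rule is wrong as written for participants who start every-2-month dosing in the study. Each such participant who is perfectly adherent loses at least one of five injections (Month 2), and four of five if targets are anchored on baseline.

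These per-participant results rest only on Annex 1, the footnote and the calendar. The group figures rest on assumed shares: 97.6% to 88.9% (rolling) or 90.2% to 55.6% (anchored) for starters making up 10% to 50% of bi-monthly participants.

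The primary endpoint is untouched. So are participants already on every-2-month dosing, including those whose loading dose came before the study: their baseline target is one month after that dose and their later targets follow at two months. This must be fixed before fidelity is reported.

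**What to change.** Reconcile the footnotes to Tables 8 and 9 with both every-2-month rows of Annex 1, so that each follow-up target used for scoring comes from the row that applies to the participant, and state how targets iterate. Re-run Tables 8 and 9 and the staff SAP fidelity metric. Check whether the show-rate window uses the same dates; if so, re-run the show rate and the feasibility composite. This concerns scoring only and takes no view on which dosing schedule is right.

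While the footnote is open, a minor labelling conflict can be settled. Section 4 of the participant SAP and the Table 8 label count injections not completed in window, grouped by missed injections, whereas the footnote sets missed injections to missing. Separate rows for late or early injections and for injections not given would resolve it, with the fidelity proportion kept per injection given.

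The cost is footnote and programming edits. The tables already use injection dates, regimen and prior CABENUVA use, so no new data are needed.

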Appendix A. Missing Data

Table A1. Summary of Missing Data

Timepoint	ltem	Completed n(%)	Missing n(%)
	FIM Item 1	n (%)	n (%)
	FIM Item 2	n (%)	n (%)
	FIM Item 3	n (%)	n (%)
Baseline	FIM Item 4	n (%)	n (%)
N=XX	AIM Item 1	n (%)	n (%)
	AIM Item 2	n (%)	n (%)
	AIM Item 3	n (%)	n (%)
	AIM Item 4	n (%)	n (%)
	FIM Item 1	n (%)	n (%)
	FIM Item 2	n (%)	n (%)
	FIM Item 3	n (%)	n (%)
Month 3	FIM Item 4	n (%)	n (%)
N=XX	AIM Item 1	n (%)	n (%)
	AIM Item 2	n (%)	n (%)
	AIM Item 3	n (%)	n (%)
	AIM Item 4	n (%)	n (%)
	FIM Item 1	n (%)	n (%)
	FIM Item 2	n (%)	n (%)
	FIM Item 3	n (%)	n (%)
Month 8	FIM Item 4	n (%)	n (%)
N=XX	AIM Item 1	n (%)	n (%)
	AIM Item 2	n (%)	n (%)
	AIM Item 3	n (%)	n (%)
	AIM Item 4	n (%)	n (%)

Abbreviations: AIM = Acceptability of Intervention Measure; FIM = Feasibility of Intervention Measure

Table A2. Summary of Free-text Responses

A Phase 4, Open-label, Single-arm Study to Optimize Implementation of CABENUVA for the Treatment of HIV-1, for Administration in US Community-based Infusion Centers or other Alternate Sites of Administration

Statistical Analysis Plan: HIV Care Providers and Key Personal Involved in the Patients' Care (Clinical Staff) and Expert Panel

EVA-30466 | March 4, 2024 | Version 3.0

Prepared	d For:	
PPD		, GSK
PPD	, PhD PPD	, Global Implementation Research, ViiV Healthcare
Vii	Ire	
Prepared PPD		
	PhD	
PPD	, PhD MPH	
PPD	, PhD MPH	
Project (Contact:	
PPD		

Statistical Analysis Plan (SAP) Signature Page

SAP Title:

A Phase 4, Open-label, Single-arm Study to Optimize Implementation of CABENUVA for the Treatment of HIV-1, for Administration in US Community-based Infusion Centers or other Alternate Sites of Administration.

Statistical Analysis Plan: HIV Care Providers and Key Personal Involved in the Patients' Care (Clinical Staff) and Expert Panel

SAP Date and Version: March 4th, 2024; Version 3.0

This SAP with the title, number, and version indicated above has been reviewed and approved by the Evidera Principal Investigators and Project Managers.

PPD	
	 Date
	 Date
	 Date
	 Date

Table of Contents

1	INTRODUCTION	1
2	STUDY DESIGN	3
	2.1 Description of the HIV Care Provider/Clinical Staff and Expert Panel Questionnaire and Schedule for Completion	4
	2.1.1 Feasibility of Intervention Measure	5
	2.1.2 Acceptability of Intervention Measure	5
	2.1.3 HIV Care Provider/Clinical Staff Additional Questionnaire	5
	2.1.4 Expert Panel Additional Questionnaire	5
3	STATISTICAL METHODS	5
	3.1 Missing Data Handling Scheme	6

eCRF	Electronic case report form
FDA	Food and Drug Administration
FIM	Feasibility of Intervention Measure
FPFV	First participant first visit
HIV	Human immunodeficiency virus
НМО	Health Maintenance Organization
IC	Infusion center
IM	Intramuscular
M3	Month 3
M4	Month 4
M6	Month 6
M8	Month 8
OCR	Optical character recognition
PDF	Portable document format
PLWHIV	Participants living with human immunodeficiency virus
POT	Plan of treatment
QAP	Qualitative analysis plan
SAP	Statistical analysis plan
SD	Standard deviation
SoA	Schedule of Activities

1 Introduction

CABENUVA is a two-drug, co-packaged product of cabotegravir plus rilpivirine, both administered as long-acting, intramuscular (IM) injections once-monthly or every two months; it is an approved treatment for human immunodeficiency virus (HIV). Clinical trial results have shown that CABENUVA administered oncemonthly or every two months is non-inferior to daily oral treatment for HIV.

Long-acting injectable treatments require changes in how HIV care is delivered. People living with HIV must attend appointments for their injections once a month or every two months, rather than seeing their providers several times per year for a prescription refill and monitoring visits. This poses new healthcare delivery challenges, including a shift in resources to this alternative means of delivering and receiving treatment —thus requiring the expansion of alternative injection facilities to include infusion centers (ICs) or alternate sites of administration (ASA). This has the potential to impact workload capacity for these facilities, though it also has the potential to positively impact treatment engagement and retention for people living with HIV.

ICs/ASA are an appealing option that can ease the burden of additional appointments, administrative work, and drug ordering in HIV specialty clinics, as well as provide people living with HIV with greater flexibility in where they receive their once monthly or every two monthly injections. In this study, the intervention itself is the process of using an IC/ASA as the location to receive the CABENUVA IM injections. Specifically, the acceptability and feasibility of injection delivery at ICs/ASAs will be assessed from the perspectives of the participants living with HIV (PLWHIV), HIV care providers/clinical staff, and IC/ASA staff.

This statistical analysis plan (SAP) describes analyses for the acceptability and feasibility of an IC/ASA to deliver CABENUVA IM injections, as reported by HIV care providers/clinical staff, as well as a tailored questionnaire that asks HIV care providers/clinical staff about their general practice history as well as their experience, attitudes, and expectations regarding the IC model of administration of CABENUVA.

This SAP will also evaluate the feasibility, acceptability, and the process of CABENUVA administrations at ICs from the Expert Panel. The Expert Panel will generate an implementation blueprint and consist of HIV care providers referring patients living with HIV to an IC/ASA, IC staff members involved in decision-making and/or oversight of daily operations, and ViiV.

This is one of four SAPs for the following protocol: *Phase 4, open-label, single arm study to optimize implementation of CABENUVA for the treatment of HIV-1, for administration in US community-based infusion centers or alternate sites of administration*. The three additional SAPs are:

- (1) analyses for the IC staff questionnaires, A Phase 4, open-label, single arm study to optimize implementation of CABENUVA for the treatment of HIV-1, for administration in US community-based infusion centers or alternate sites of administration, Statistical Analysis Plan: IC Staff;
- (2) analyses of questionnaires for PLWHIV, A Phase 4, open-label, single arm study to optimize implementation of CABENUVA for the treatment of HIV-1, for administration in US community-based

infusion centers or alternate sites of administration, Statistical Analysis Plan: Participants living with HIV for Implementation Science Questionnaires; and

(3) analyses for clinical data for PLWHIV, A Phase 4, open-label, single arm study to optimize implementation of CABENUVA for the treatment of HIV-1, for administration in US community-based infusion centers or alternate sites of administration: Statistical Analysis Plan for Clinical Analyses.

While there are no primary objectives involving HIV care providers/clinical staff or the Expert Panel for this study, this SAP will describe the planned secondary quantitative objectives related to HIV care providers/Expert Panel as outlined in Table A. Additionally, this plan does not incorporate the qualitative interview analyses at the end of study. These analyses will be detailed in a separate qualitative analysis plan (QAP) (currently under development).

Table A. Objectives and Endpoints for HIV Care Providers/Clinical Staff and the Expert Panel

Objectives	Endpoints
	Proportion of HIV care providers/clinical staff that agree or completely agree (a score of 4 or higher) across all items on the FIM at Month 1, Month 4 and at Month 8
To evaluate feasibility of CABENUVA administration at infusion centers or	Change over time in the FIM at Month 4 and Month 8 with HIV care providers/clinical staff
alternate sites of administration HIV care providers/ clinical staff	Summary of other quantitative questionnaires assessed with HIV care providers/clinical staff at Month 1, Month 4 and Month 8
	Qualitative interviews assessed at Month 8 with HIV care providers/ clinical staff (QAP)
	Proportion of HIV care providers/clinical staff that agree or completely agree (a score of 4 or higher) across all items on the AIM at Month 1, Month 4 and Month 8
To evaluate acceptability of CABENUVA administration at infusion centers or alternate sites of	Change of HIV care providers/clinical staff over time in the AIM at Month 4 and Month 8
administration from HIV care providers/clinical staff	Summary of other quantitative questionnaires assessed with HIV care providers/clinical staff at Month 1, Month 4 and Month 8
	Qualitative interviews assessed at Month 8 with HIV care providers/clinical staff (QAP)
To evaluate feasibility, acceptability and the process of CABENUVA	Proportion of Expert Panel that agree or completely agree (a score of 4 or higher) across all items on the FIM and AIM respectively prior to FPFV, and at Month 3 and Month 6
administration at infusion centers or	Change of Expert Panel over time in FIM and AIM respectively through Month 6
alternate sites of administration from the Expert Panel	Summary of other quantitative questionnaires assessed with Expert Panel prior to FPFV, and at Month 3 and Month 6
	Qualitative interviews assessed with Expert Panel prior to FPFV and at Month 6 (QAP)
To evaluate perceptions, facilitators, and barriers/concerns by HIV care	Qualitative interviews assessed at Month 8 with HIV care providers/clinical staff (QAP)
providers/clinical staff	Summary of HIV care provider/clinical staff other quantitative questionnaires at Month 1, Month 4, and Month 8
To assess the advantages to receive or	Qualitative interviews assessed at Month 8 with HIV care providers/clinical staff (QAP)
refer participants to receive CABENUVA at the infusion center or alternate sites of administration or	Summary of advantage to referring participants to the IC/ASA to receive CABENUVA at Month 1, Month 4, and Month 8 assessed by HIV care provider other quantitative questionnaires

Objectives	Endpoints		
alternate site of administration from HIV care providers/clinical staff			
To assess the disadvantages about receiving CABENUVA at the infusion center or alternate sites of	Summary of disadvantage of referring participants to IC/ASA for CABENUVA injections from HIV care providers/clinical staff other quantitative questionnaires at Month 1, Month 4 and Month 8		
administration or alternate site of administration from HIV care providers/clinical staff	Qualitative interviews assessed at Month 8 with HIV care providers/clinical staff (QAP)		
To evaluate the acceptability of receiving and referring participants for CABENUVA injections at infusion centers or alternate sites of	Summary of acceptability of the process of referring participants to the infusion center or alternate sites of administration for CABENUVA by HIV care providers/clinical staff other quantitative questionnaires at Month 1, Month 4, and Month 8		
administration from HIV care providers/clinical staff	Qualitative interviews assessed at Month 8 with HIV care providers/clinical staff (QAP)		
To evaluate the usefulness of the POT	Summary of usefulness of the POT by HIV care providers/ clinical staff other quantitative questionnaires at Month 4 and Month 8		
for HIV care providers/clinical staff	Qualitative interviews assessed at Month 8 with HIV care providers/clinical staff (QAP)		
To evaluate overall opinion of receiving and administering the injection at an infusion center or alternate sites of administration by HIV care providers/clinical staff	Qualitative interviews at Month 8 with 00000HIV care providers/clinical staff (QAP) Summary of overall opinion of referring patients to an IC center for CABENUVA injections by HIV care provider/clinical staff via other quantitative questionnaires at Month 1, Month 4 and Month 8		

Abbreviations: AIM = Acceptability of Intervention Measure; ASA=Alternative Site of Administration; FIM = Feasibility of Intervention Measure; FPFV = first participant first visit; HIV = human immunodeficiency virus; IC = infusion center; POT = plan of treatment; QAP = qualitative analysis plan

2 Study Design

This is a Phase 4, single arm, open-label, multi-center study examining the administration of CABENUVA IM in IC/ASAs in the United States. This study is being conducted following Food and Drug Administration (FDA) approval and commercial availability of CABENUVA. Eligible and consenting participants will be followed for eight months to evaluate an implementation blueprint for IM administration of CABENUVA for HIV-1 treatment at ICs/ASAs. The total duration for study participants is approximately eight months from the time of enrollment and receipt of the first administration of CABENUVA IM injections at the ICs/ASA.

Relevant to this SAP, approximately 20 HIV care providers/clinical staff who refer their patients living with HIV to a study ICs/ASA to receive CABENUVA will be asked to complete questionnaires per the Schedule of Activities (SoA, see ANNEX 1 in protocol) after the HIV care provider's first referred patient is enrolled into the study. This study also has an Expert Panel, consisting of approximately 10 members, which will consist of key ICs/ASA staff members involved in decision making and/or oversee daily operations at the ICs/ASA, selected HIV care providers that may refer PLWHIV, and ViiV. Panel members will meet prior to Baseline/Month 1 to design the Blueprint.

The duration of study participation for each HIV care provider/clinical staff is approximately 8 months after their last PLWHIV has their first visit (last participant first visit) and receives CABENUVA IM injections at a participating ICs/ASA. HIV care provider/clinical staff and Expert Panel questionnaires consist of the Feasibility of Intervention Measure (FIM) and the Acceptability of Intervention Measure (AIM) and additional tailored questions. HIV care providers/clinical staff will be asked to complete the Baseline/Month 1 questionnaire within four weeks of their first referred participant's first visit (FPFV) in the study at any study site. Month 4 and Month 8 assessments are to be completed when the HIV care provider's/clinical staff first referred patient completes the Month 4 or Month 8 study visits, respectively. Questionnaires can be completed up to two weeks before or after the Month 4 or Month 8 study visits. The Expert Panel will be asked to complete the Baseline/Month 1 questionnaire prior to the FPFV, defined as the date when a participant signs the informed consent form, completes protocol procedures, and receives the first CABENUVA injections at any IC/ASA. Month 3 and Month 6 assessments are to be completed after approximately 10 participants (across all ICs/ASAs) have completed their Month 3 and Month 6 study visits at any IC/ASA site.

2.1 Description of the HIV Care Provider/Clinical Staff and Expert Panel Questionnaire and Schedule for Completion

The HIV care provider/clinical staff questionnaire consists of two validated instruments and tailored items written for this study. The validated instruments are the FIM and AIM, described below. The tailored items ask HIV care providers/clinical staff about several topics including, but not limited to, their practice, experience, and views on the CABENUVA / long-acting injectable model, as well as using ICs/ASAs to implement that model. The Expert Panel questionnaire also consists of the FIM and AIM and tailored items. Two different versions of the FIM and AIM will be used for the Expert Panel: one for HIV care providers/clinical staff and one for IC/ASA staff. Across FIM and AIM versions, the stem of each item has slightly different wording, reflecting the different roles of HIV care providers/clinical staff and IC/ASA staff. Response options are the same across versions. Due to the small numbers on the Expert Panel, the FIM and AIM will be summarized in all tables together, though the differences in the wording for underlying groups, due to their different roles, should be noted. The tailored items will ask the Expert Panel about the specifics of the implementation of the study.

A feasibility composite score for HIV care providers/clinical staff and Expert Panel, to be determined, will be added to this SAP. The exact components of the feasibility composite score will be informed by the Expert Panel process to ensure it matches the critical variables identified by all members of the panel.

Table B. Questionnaire Administration for HIV Care Provider/Clinical Staff and Expert Panel

Questionnaire	Baseline	Month 3	Month 4	Month 6	Month 8
HIV Care Provider Tailored Items, HIV Care Provider/ Clinical Staff	Х		Х		х*
Feasibility of Intervention Measure, HIV Care Provider/ Clinical Staff	Х		Х		х
Acceptability of Intervention Measure, HIV Care Provider/ Clinical Staff	х		х		х
Feasibility of Intervention Measure, Expert Panel	Х	Х		Х	

Questionnaire	Baseline	Month 3	Month 4	Month 6	Month 8
Acceptability of Intervention Measure, Expert Panel	Х	Х		Х	

Abbreviation: HIV = human immunodeficiency virus

